6.2 Freedom from TLR

Target lesion information will be obtained from 'Core Lab Analysis – Angio Re-Intervention Analysis' CRF page. If for some reason the Angio data is missing, but there was TLR reported by site then Site Re-Intervention data will be used from 'Target Vessel Re-Intervention' CRF page. Freedom from TLR will be analyzed by subject at 30 days, 6 months, and 12 months visit.

Evaluable subjects: To be included in the denominator at a particular visit, the subject should have been followed-up beyond the beginning of the lower end of the respective visit window (23 days for 30 days, 150 days for 6 months, and 335 days for the 12 months) or the subject should have had a TLR event before the upper limit of visit window (37 days for 30 days, 210 days for 6 months, and 395 days for the 12 months).

The TLR (Re-intervention date) is based on the following definition:

TLR duration = (Date of TLR - Date of Index Procedure).

Failure: Subject has a failure event if Target Lesion Re-Intervention occurred before the upper limit of the respective visit window (Core Lab Angio CRF page). If TLR was reported by site but was missing in the Core lab page, then use Target Lesion Revascularization occurred before the upper limit of the visit window (Site Re-Intervention CRF page) as failure.

Success: Subject has no failure event and is an evaluable subject as defined above.

Kaplan-Meier Analysis:

In addition to the analyses that are proportion-based, survival analysis will be performed (Kaplan-Meier estimate of survival function). Freedom from TLR at 30 days, 6 months, and 12 months: the time to first event will be the time from index-procedure to the first occurrence

of the first failure event, all subjects who have succeeded the TLR endpoint will be censored at Day 395 if not discontinued (discontinued subjects will be censored at discontinuation day), and all the subjects with missing TLR endpoint will be censored at the last available study day.

Binary outcome and Kaplan-Meier analyses for ATK, BTK and All UltraScore[™] subjects will be provided for the ITT population.

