6.3 Freedom from Major Amputation (Above the Ankle)

Freedom from major amputation of target limb (above the ankle) will be reported at 30 days, 6 months, and 12 months using data from 'Target Limb Amputation' CRF page.

Evaluable subjects: To be included in the denominator at a particular visit, the subject should have been followed-up beyond the beginning of the lower end of the respective visit window (23 days for 30 days, 150 days for 6 months, and 335 days for the 12 months) or the subject should have had a major amputation of target limb (above the ankle) event before the upper limit of visit window (37 days for 30 days, 210 days for 6 months, and 395 days for the 12 months).

The freedom from major amputation is based on the following definition:

Major amputation duration = (Date of Amputation - Date of Index Procedure).

Failure:Subject has a failure event if Major amputation of target limb is above the ankle
which includes Below knee or Through Knee or Above Knee.

Success: Subject has no failure event and is an evaluable subject as defined above.

Kaplan-Meier Analysis:

In addition to the analyses that are proportion-based, survival analysis will be performed (Kaplan-Meier estimate of survival function). Freedom from major amputation at 30 days, 6 months, and 12 months: the time to first event will be the time from index-procedure to the first occurrence of the first failure event, all subjects who have succeeded the major amputation endpoint will be censored at Day 395 if not discontinued (discontinued subjects will be censored at discontinuation day), and all the subjects with missing major amputation endpoint will be censored at the last available study day.

Binary outcome and Kaplan-Meier analyses for ATK, BTK and All UltraScore[™] subjects will be provided for the ITT population.

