7.3.2 Assessment of Secondary Endpoints for subjects with DCB used at baseline

Freedom from TLR and major amputation will be separately reported for ATK, BTK and All UltraScore[™] subjects with DCB used at baseline either before or after ultrascore.

Primary patency will be reported for ATK subjects with DCB used at baseline either before or after ultrascore.

Secondary endpoints and evaluable subjects are as defined in section 6.2, 6.3 and 6.5, respectively, with an additional requirement that the subjects have had DCB at index procedure.

7.3.3 Assessment of death for subjects with DCB used at baseline either before or after ultrascore

Freedom from death will be reported at 30 days, 6 months, and 12 months using data from 'Subject Disposition' CRF page.

Evaluable subjects: To be included in the denominator at a particular visit, the subject should have had DCB as adjunctive treatment either before or after Ultrascore and been followed-up beyond the beginning of the lower end of the respective visit window (23 days for 30 days, 150 days for 6 months, and 335 days for the 12 months) or the subject should have had died before the upper limit of visit window (37 days for 30 days, 210 days for 6 months, and 395 days for the 12 months).

Death duration = (Date of Death - Date of Index Procedure).

8 Statistical Analyses of Adverse Events and Device Deficiencies

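### The proportions for freedom from TLR, major amputation and death keep early leavers only if they had the event; this modestly overstates 12-month event rates when dropout is non-informative, and for death no other estimator is planned

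*SAP*

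**What the plan says.** SAP 6.2 gives two routes into the denominator for freedom from TLR. In the first, "the subject should have been followed-up beyond the beginning of the lower end of the respective visit window": day 23, 150 or 335. The second is an alternative to it: "or the subject should have had a TLR event before the upper limit of visit window", that is, day 37, 210 or 395.

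SAP 6.3 repeats the rule for amputation, its second route being that "the subject should have had a major amputation of target limb (above the ankle) event before the upper limit of visit window".

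SAP 7.3.3 repeats it for death in a restricted population: "the subject should have had DCB as adjunctive treatment either before or after Ultrascore", with the same lower bounds, "or the subject should have had died before the upper limit of visit window". The planned output is brief: "Freedom from death will be reported at 30 days, 6 months, and 12 months using data from" the disposition CRF page. The section gives a duration formula but names no Kaplan-Meier estimate and no confidence interval.

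For TLR and amputation, SAP 6.2 and 6.3 add a second analysis: "survival analysis will be performed (Kaplan-Meier estimate of survival function". Event-free subjects who have not discontinued are censored at Day 395, and discontinued subjects on the day they discontinue. Neither section says which analysis is the main result, and neither specifies a confidence interval.

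Protocol 6.5 lists death as a reason for discontinuation and says that leavers are not replaced. Protocol 7.3 bases rates on available data without imputation. Neither document gives an expected event rate or dropout rate.

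**The concern.** Entry to the denominator depends on the outcome. Take two subjects who both leave at month 4. The one who already had a TLR counts as a failure at 12 months; the one who had none is removed. The resulting proportion is neither the risk among all treated subjects nor the risk among completers. A subject who dies free of TLR before day 335 also drops out of the 12-month TLR proportion.

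The distortion grows with attrition. Results are shown side by side for the above-the-knee (ATK) and below-the-knee (BTK) cohorts (SAP 7.1), so unequal loss could by itself produce a small apparent difference between them.

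For TLR and amputation a reader has Kaplan-Meier as a second estimate. For death, the proportion in 7.3.3 is the only one.

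**Working it through.** The plan states no figure to reproduce. Event and attrition rates below are assumptions.

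**Set-up.** The event hazard λ is constant, with true day-365 rate r, so λ = −ln(1−r)/365. The dropout hazard μ is constant and independent of risk, with a share a leaving before day 335, so μ = −ln(1−a)/335. Final visits are spread evenly over days 335 to 395 (SAP window). Let h = λ + μ.

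- Events observed by day 335: E1 = (λ/h)(1 − e^(−335h))
- Event-free and still followed at day 335: S = e^(−335h)
- Events observed after day 335: E2 = S·λ·[1/h − (1 − e^(−60h))/(60h²)]
- Proportion under the SAP rule: (E1 + E2)/(E1 + S)

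**Worked case, r = 10%, a = 20%.** λ = 0.00028866, μ = 0.00066609, h = 0.00095475. Then S = 0.7263, E1 = 0.0828 and E2 = 0.0062. The proportion is 0.0889/0.8090 = 10.99%. In a cohort of 175 (SAP 3.3) that is about 15.6 events among 141.6 evaluable subjects; the other 33.4 left event-free and are dropped.

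| True day-365 rate | Attrition | SAP proportion | Excess (points) |
|---|---|---|---|
| 10.0% | 0% | 10.00% | 0.00 |
| 10.0% | 10% | 10.45% | 0.45 |
| 10.0% | 20% | 10.99% | 0.99 |
| 10.0% | 30% | 11.65% | 1.65 |
| 25.0% | 10% | 25.96% | 0.96 |
| 25.0% | 20% | 27.10% | 2.10 |
| 25.0% | 30% | 28.46% | 3.46 |

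Simulation of the same situation gives 10.5%, 11.1% and 11.6%, and 26.0%, 27.2% and 28.5%: agreement to about 0.1 point. In relative terms the excess is roughly half the attrition share. The formula applies unchanged to death.

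**Cohort contrast.** Two cohorts with the same true 10.0% and attrition of 10% and 30% would show 10.45% and 11.65%, an apparent gap of 1.2 points.

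**Precision.** The 95% half-width with 175 subjects is 1.96·√(0.10·0.90/175) = 4.4 points at 10%, and 1.96·√(0.25·0.75/175) = 6.4 points at 25%.

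**Kaplan-Meier as written.** A completer last seen at day 340 stays in the risk set to Day 395. With evenly spread final visits, at day 335 + u a share of about u/60 of the nominal risk set is no longer observed, so the estimated hazard is about λ(1 − u/60). To day 365 this counts 30 − 900/120 = 22.5 days instead of 30. The estimate is 1 − e^(−357.5λ) = 9.8% against a true 10.0%. Censoring at last contact returns 10.0%.

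**Sensitivity of the direction.**
- Against day-395 risk, 1 − e^(−395λ) = 10.78%, the proportion at 10% attrition (10.45%) is too low, because event-free exits from day 335 on count as successes. At 20% attrition (10.99%) it is slightly too high.
- If leavers' event hazard is about 2.0 to 2.6 times that of stayers (5–20% events, 5–20% dropout), the overstatement of the day-365 rate disappears; beyond that it reverses.

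**The case against.** The case for leaving the text alone is substantial. Kaplan-Meier is already planned for TLR and amputation, in both cohorts and overall, with discontinued subjects censored when they leave. The proportion follows the protocol's available-data rule, and the SAP presents Kaplan-Meier as an addition to it. There is no hypothesis test, these are not primary endpoints, and the cohort results are descriptive. The shift is well inside sampling error, and its direction requires non-informative dropout. The death analysis is a supplementary table in a subset, and deaths also appear among discontinuation reasons (SAP 9.7).

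Most of this stands, and it limits the size and importance of the point. It does not remove the outcome-dependent denominator. A count of deaths by discontinuation reason is not an estimate of freedom from death at a given time.

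A reader might infer that the proportion is too high and Kaplan-Meier too low, so that the two planned figures lie on opposite sides of the truth. That depends on the time point and on when final visits occur. Against day 365 with visits spread over the window, they do. If every completer is seen to day 395, Kaplan-Meier at day 395 is unbiased. With spread visits and 10% attrition, both lie below the day-395 risk: 10.45% and, from 335 + 30 counted days, 1 − e^(−365λ) = 10.0%, against 10.78%. The documents do not support a general statement.

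**Conclusion.** The point holds at modest size. In SAP 6.2, 6.3 and 7.3.3, subjects lost before the window count only if they had the event. With non-informative dropout the proportion overstates the day-365 event rate by about 0.5 to 1.7 points at a true 10%, and by about 1.0 to 3.5 points at a true 25%, for 10% to 30% attrition. These rates are assumed. The unqualified reading that reported event rates will be too high is not supported: the bias can be absent or reversed against day-395 risk at low attrition, or when leavers are at much higher risk.

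For TLR and amputation, what remains is that no main estimate is named and that Day 395 censoring slightly understates events when final visits fall earlier. For death the gap is plainer, since only the proportion is planned.

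**What to change.** - **SAP 7.3.3:** add a Kaplan-Meier estimate of freedom from death with a 95% CI at 30 days, 6 months and 12 months, censoring survivors at last contact.
- **SAP 6.2 and 6.3:** censor event-free subjects at last contact instead of Day 395, and name Kaplan-Meier with its 95% CI as the main figure.
- **All three sections:** keep the proportion as a supportive table, showing how many subjects the evaluable rule excludes at each visit.
- **Deaths without TLR or amputation:** these would be censored in Kaplan-Meier, so the change does not by itself deal with them. Show their number, or add a cumulative incidence estimate with death as a competing event.

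The cost is SAP wording and one added table for death, plus the cumulative incidence output if chosen. The procedure, event, death and last-visit dates are already used in the SAP, so no new data are needed. The downside is that the main figure then relies on non-informative censoring; the supportive table and the excluded counts show readers how much rests on that.

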6.4 Subject Follow-Up

All study subjects are to be followed according to the investigational site's standard of care practices. In addition to the standard of care visits, study participants will either return to the site or be reached by telephone at the following intervals:

- *Follow-up Contact 1*: 30 ± 7 days post-procedure;
- *Follow-up Contact 2:* 6 months ± 30 days post-procedure;
- *Follow-up Contact 3:* 12 months \pm 30 days post-procedure.

Subjects with a treated ATK target lesion will return to the site to undergo a Duplex Ultrasound (DUS) performed at 30 days and 6 and 12 months post-index procedure. DUS imaging of the target lesion employing the "Ultrasound Guidelines" shall be uploaded or sent to the core laboratory for analysis.

Subjects with a treated BTK target lesion will return to the site for a standard of care clinical evaluation at 30 days and 6 and 12 months post-index procedure. DUS is not required for BTK subjects.

The following will be collected during follow-up and documented in the subject's medical record at the site:

- *Documentation of Status:* Determine and document whether the subject has undergone a TLR or target vessel revascularization (TVR), amputation procedure since last contact, and antiplatelet/anticoagulation medications. Angiographic imaging of any TLR/TVR must be sent to the angiographic core lab for analysis. Measurement of target limb ABI and Rutherford Classification.
- *Documentation of AEs:* Documentation of occurrence of AEs since last followup (see Section 8).

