6.5 Subject Discontinuation

Following the index procedure, subjects should remain in the study until completion of required follow-up. The follow-up period for this study is 12 months (365 ± 30 days).

However, a subject's participation may be discontinued. Potential reasons for discontinuation may include, but are not limited to the following:

- Lost to Follow-Up (LTF): A subject may be considered LTF if the site personnel are unable to locate the subject despite two documented attempts to notify the subject via telephone and a third attempt by certified mail. This does not apply to missed visits, where the subject misses one of the follow up contact time points, but completed a subsequent one (when a subject misses two consecutive follow-ups with failure of contact attempt, the subject may be considered LTF and withdrawn from the study). Before the site considers a subject LTF, written agreement should be obtained from the Sponsor.
- *Withdrawn Consent:* The subject requests to terminate his/her participation in the study (the Investigator must attempt to identify and document the reasons for termination).
- *Death:* The subject becomes deceased. If known, the cause of death must be documented (see Section 8.5).
- *Withdrawal by Investigator:* Participation may be immediately terminated by the Investigator if, in the opinion of the Investigator, the subject would be exposed to inappropriate risk by continuing in the study. Additionally, the Investigator may terminate a subject's participation with prior written approval from the Sponsor if the subject is repeatedly noncompliant with study procedures.
- *Study Termination:* The study is terminated by the Sponsor (see Section 11.9).

Additional subjects will not be enrolled to replace those who withdraw from the study.

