In addition to the analyses that are proportion-based, survival analysis will be performed (Kaplan-Meier estimate of survival function). Primary patency of the target lesion for ATK subjects at 30 days, 6 months, and 12 months, the time to first event will be the time from index-procedure to the first occurrence of the first failure event, all subjects who have succeeded the primary patency endpoint will be censored at Day 395 if not discontinued (discontinued subjects will be censored at discontinuation day), and all the subjects with missing primary patency endpoint will be censored at the last available study day.

Binary outcome and Kaplan-Meier analyses for ATK subjects will be provided for the ITT population.

6.6 Restenosis for ATK Subjects Late for More Than 30 Days at 12-Month Visit due to COVID-19 (as measured by DUS Core Lab)

Restenosis of the target lesion for ATK subjects late for more than 30 days at 12-month visit due to covid-19 will be reported using Target Lesion DUS Stenosis category (recorded from the 'Core Lab Analysis – DUS Image Findings' CRF page) by subject.

Evaluable subjects: To be included in the denominator, the subject should have been late for more than 30 days at the 12-month visit (more than 395 days since index procedure) due to COVID-19 (identified via Protocol Deviation and Study Visit CRFs) and had a valid stenosis category result (patent, 50-99%, or occluded) in the DUS for the visit.

Restenosis: Subject has restenosis if the stenosis category for Target Lesion as adjudicated by Core Lab DUS is occluded or 50-99%.

7 Statistical Analysis of Subgroup Analyses

7.1 Primary and Secondary Endpoints for Above the Knee (ATK) and Below the Knee (BTK) subjects

The primary and secondary endpoints will be presented descriptively for ATK and BTK subjects. The endpoints and statistical methods will be similar to section 5 and section 6.

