9.6 Follow-up Period

The duration of follow-up period after Index procedure during the study will be reported for ATK, BTK and All UltraScoreTM subjects and calculated as:

(Date of the last study visit – Date of the index procedure).

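### The Kaplan-Meier rule for TLR and major amputation keeps completers at risk to Day 395, up to 60 days past their last planned contact

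*SAP*

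**What the plan says.** SAP 6.2 gives the Kaplan-Meier censoring for freedom from TLR: "all subjects who have succeeded the TLR endpoint will be censored at Day 395 if not discontinued (discontinued subjects will be censored at discontinuation day". SAP 6.3 does the same for the other event endpoint: "all subjects who have succeeded the major amputation endpoint will be censored at Day 395 if not discontinued". In both sections, subjects with a missing endpoint are censored at their last available day.

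Four other places bear on this:

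- **Who is a success (SAP 6.2 and 6.3).** The subject must be event-free and "followed-up beyond the beginning of the lower end of the respective visit window". For the 12-month visit that limit is Day 335.
- **How events are found (Protocol 6.4).** At each contact the site must "Determine and document whether the subject has undergone a TLR or target vessel revascularization (TVR), amputation procedure since last contact". No contact is planned after the 12-month one.
- **When follow-up ends (Protocol 6.5).** "The follow-up period for this study is 12 months (365 ± 30 days").
- **Who counts as discontinued (SAP 9.7).** Completed and discontinued are separate disposition categories, so a completer falls under the Day 395 rule.

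The SAP does not say on which day the 12-month Kaplan-Meier estimate is read.

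**The concern.** Kaplan-Meier estimation assumes that everyone counted at risk on a given day would have had an event on that day recorded. Here that fails from Day 335 onward. A completer whose final visit is Day 340 stays in the risk set for 55 further days with no planned contact to capture an event. A subject who is a success and discontinues on Day 340 has the same observed follow-up but is censored on Day 340. SAP 9.6 also measures follow-up as "Date of the last study visit – Date of the index procedure", which for the completer gives 340 days, not 395.

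The number at risk late in the curve would then include subjects no longer followed, and the standard error would be smaller than the data support. The curve would lie above true survival on any day that some final visits precede. Because the reading day is not fixed, that choice also stays open until after the data are seen.

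**Working it through.** **Window arithmetic.** 365 − 30 = 335 and 365 + 30 = 395, which reproduces the SAP's limits. The largest unobserved credit is 395 − 335 = 60 days. With visits uniform over the window the average is 30 days. At a Day 365 reading at most 365 − 335 = 30 of these days count.

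**Inputs.** From the documents: n = 350 (planned maximum) and the Day 335–395 window. Assumed, because the documents give no figure: 12% dropout uniform over Day 0–335, constant hazard, true 12-month freedom from TLR of 90, 80 or 70%, and three patterns of visit timing.

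**Approximate formula.** With λ = −ln(S)/365, only subjects not yet seen for their final visit can contribute events after Day 335, but all are counted at risk. The estimate at Day 365 is then about exp(−λ(335 + d)), where d is the average number of observed days between Day 335 and Day 365. For visits uniform over Day 335–395, half the subjects contribute 30 days and half contribute 15 on average, so d = 22.5.

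Worked case, S = 0.80: λ = 0.22314/365 = 0.000611. The rule gives exp(−0.000611 × 357.5) = 0.8037 against a true 0.8000, or +0.37 points.

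| 12-month visits | d (days) | Error at Day 365, S = 90/80/70% (points) |
|---|---|---|
| uniform Day 335–395 | 22.5 | +0.20 / +0.37 / +0.51 |
| uniform Day 335–365 | 15 | +0.39 / +0.74 / +1.03 |
| all on Day 335 (extreme) | 0 | +0.78 / +1.48 / +2.08 |
| all after Day 365 | 30 | 0 |

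**Simulation** (4000 replicates, with dropout). The errors are +0.2/+0.4/+0.5 with uniform visits, +0.4/+0.7/+1.0 with all visits by Day 365, and none with all visits after it. The sampling SD is 1.6/2.2/2.5. At 80% with a falling or rising hazard (Weibull shape 0.7 to 1.5) the error is +0.2 to +0.6 with uniform visits and +0.6 to +1.2 with all visits by Day 365.

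**Number at risk, 80%, uniform visits.** After dropout, 350 × 0.88 = 308 remain. At Day 365 the rule carries 308 × 0.8037 ≈ 248, while those still followed are 308 × 0.80 × 0.5 ≈ 123. At Day 390 the simulated figures are 246 and 20.

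**Precision, same case:**

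| Day | SE: SAP rule vs last contact | Coverage of 95% CI for same-day survival |
|---|---|---|
| 365 | 2.19 vs 2.25 | 94.0% vs 94.9% |
| 390 | 2.21 vs 2.54 | 90.0% vs 94.4% |

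**Reading day.** If the curve is read at Day 395 and labelled 12 months, the simulated error against the true Day 365 value (90/80/70%) is 0.0 with uniform visits, +0.4/+0.7/+1.0 with all visits by Day 365, and −0.4/−0.8/−1.0 with all visits after it. The sign depends on visit timing.

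**Amputation.** At an assumed 98% freedom the error at Day 365 is at most 0.1 point.

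**The case against.** The strongest reply is that the remedy does not reduce total error. At 80% with uniform visits, RMSE at Day 365 goes from 2.21 to 2.24. If all visits fall by Day 365 it goes from 2.3 to 2.9, with almost nobody left at risk. That stands.

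Day 395 is also the SAP's own upper limit for counting 12-month events, and under uniform visits a Day 395 reading is unbiased for the 12-month value. That stands too, but only for that visit pattern, and the SAP does not name Day 395 as the reading day.

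Sixty days is a maximum, and Day 390 is not a reporting time. SAP 6.6 expects some ATK visits after Day 395 because of COVID-19, and those subjects are truncated at Day 395, not over-credited. If 25% or 50% of subjects were late (assumed), the Day 365 error at 80% would fall from 0.37 to 0.28 or 0.17 points. SAP 9.6 is a descriptive summary of follow-up, not a censoring rule. The endpoints are secondary and there is no hypothesis.

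All this limits the size. It does not answer the point that the rule counts unfollowed subjects as at risk and treats two subjects with identical follow-up differently.

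**Conclusion.** The concern holds. As written, SAP 6.2 and 6.3 credit non-discontinued, event-free subjects with up to 60 days that no planned contact covers, and nothing elsewhere in either document limits this. On the assumptions above, the TLR estimate at Day 365 is high by 0.2 to 0.5 points with uniform visits, by up to about 1 point if all visits fall by Day 365, and not at all if all fall after it. Each figure is below one sampling SD. The clearer faults are the number at risk, about double the true figure at Day 365 and twelve times it at Day 390 in the 80% case, and a late-curve standard error that is too small.

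The stakes are minor to moderate. The 30-day and 6-month estimates are essentially untouched, the proportion-based rates do not use this censoring, and the amputation effect is negligible. The correction is for an accurate curve and risk set, not a changed conclusion.

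**What to change.** **SAP 6.2 and 6.3.** Censor event-free subjects at the earlier of last documented contact and Day 395. State that the 12-month Kaplan-Meier estimate is read at Day 365, and print the number at risk.

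Add a note that the proportion-based TLR rate runs to the end of the window ("Subject has a failure event if Target Lesion Re-Intervention occurred before the upper limit of the respective visit window"), so the two 12-month figures can differ. At 80% with uniform visits about 1.1 TLRs per 350 subjects fall after Day 365 (0 to 2.2 across visit timings), which lowers the proportion by about 0.4 points (0 to 0.7).

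**SAP 6.5, a clarification only.** The patency rule says "all the subjects with missing primary patency endpoint will be censored at the last available study day". Say whether this means last contact or last valid DUS, and report the other as a sensitivity analysis. In simulations with 175 ATK subjects, 10% discontinued, 10 to 30% of the rest without a 12-month DUS and true patency of 65 to 85%, the two readings differ by 0.9 to 5.2 points and bracket the truth. Keep the imaging-date formula and Day 395 for subjects with a patent 12-month DUS. Do not carry the Day 365 reading over to patency: scans run to Day 395, and a Day 365 reading was 2.6 to 10.3 points high in the same simulations.

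**Cost.** A few SAP sentences and reprogrammed censoring dates, using visit dates that SAP 9.6 already needs. TLR estimates become slightly less favourable. At 80% and Day 365 the SD rises from 2.17 to 2.24 with uniform visits. If all visits fall by Day 365 it rises from 2.2 to 2.9, and the mean Greenwood SE of 2.4 then understates it, which is why the number at risk must be shown.

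### Neither planned estimate of TLR or major amputation gives the share of subjects who actually have the event: Kaplan-Meier censors event-free deaths, the proportions drop the earlier ones, and no competing-risk estimate is added

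*SAP*

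**What the plan says.** SAP 6.2 (TLR) and 6.3 (major amputation of the target limb) each plan two analyses.

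- **Proportion by visit.** To enter the denominator, "the subject should have been followed-up beyond the beginning of the lower end of the respective visit window" (day 23, 150 or 335), or the subject must have had the event before the upper limit (day 37, 210 or 395).
- **Kaplan-Meier, in addition.** Subjects who succeed on the endpoint are censored at day 395, except that "discontinued subjects will be censored at discontinuation day". For the rest, "all the subjects with missing TLR endpoint will be censored at the last available study day"; SAP 6.3 has the matching clause, "all the subjects with missing major amputation endpoint will be censored at the last available study day".

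Protocol 6.5 lists death among the discontinuation reasons, next to loss to follow-up and withdrawn consent: "The subject becomes deceased. If known, the cause of death must be documented". Neither SAP 6.2 nor 6.3 mentions death, a competing-risk method or amputation-free survival.

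On mortality itself, SAP 7.3.3 plans that "Freedom from death will be reported at 30 days, 6 months, and 12 months", but only for subjects with DCB used at the index procedure. SAP 9.7 counts discontinuations by reason. On the cohorts, SAP 7.1 states: "The primary and secondary endpoints will be presented descriptively for ATK and BTK subjects".

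**The concern.** A subject who has died cannot later have a TLR or an amputation. Death is therefore a competing event, unlike a withdrawal, after which the event can still happen unseen. If deaths are censored, one minus Kaplan-Meier describes the risk that would apply if death were removed and the event hazard stayed the same. That is higher than the share of treated subjects who go on to have the event.

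The proportions do not fill the gap. A subject who dies event-free before the lower window limit leaves the denominator, while a subject who has the event and then dies stays in it as a failure.

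Both documents give the purpose as real-world outcome data for physicians. A reader will take a 12-month TLR or amputation figure as the fraction of patients to whom it happened, and no planned output gives that fraction. Nor can it be rebuilt from other tables. Deaths outside the DCB subgroup appear only as disposition counts, which are not stated to be timed or split by cohort, and AE collection is limited to device- or procedure-related events.

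**Working it through.** **Which clause governs a death (12-month endpoint).** Success requires an evaluable subject, that is, one followed beyond day 335.

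- Event-free death before day 335: not evaluable, so the endpoint is missing. Kaplan-Meier censors at the last available study day, and the proportion drops the subject.
- Event-free death after day 335: evaluable and a success. Kaplan-Meier censors at discontinuation day, and the proportion keeps the subject.

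So the last-available-day clause covers most deaths. The SAP does not say whether that day is the date of death or the last visit; if the latter, censoring comes earlier still.

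**Inputs.** From the documents: about 175 subjects per cohort, and the window limits of days 335 and 395. The documents give no TLR, amputation or mortality rate, so there is no stated figure to reproduce. Assumed: constant, independent hazards, no other dropout, 12-month mortality D of 5 to 20%, and 12-month event risk F on the Kaplan-Meier scale of 5 to 20%.

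**Formulas.** With a = −ln(1−F), b = −ln(1−D) and s = day/365:

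- one minus Kaplan-Meier = 1 − exp(−a·s)
- cumulative incidence = a/(a+b) × [1 − exp(−(a+b)·s)]
- evaluable-only proportion = incidence to day 395 ÷ (incidence to day 335 + share alive and event-free at day 335)

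**Example, F = 20%, D = 15%.** a = 0.2231, b = 0.1625, a+b = 0.3857, a/(a+b) = 0.5786. At day 365, incidence = 0.5786 × (1 − 0.6800) = 18.5%, against 20.0% for one minus Kaplan-Meier. A simulation of this case also gave 18.5%.

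**Overstatement by one minus Kaplan-Meier at day 365, in points.**

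| F | D = 5% | 10% | 15% | 20% | 95% half-width, n = 175 |
|---|---|---|---|---|---|
| 20% | 0.49 | 0.98 | 1.48 | 2.00 | 5.9 |
| 10% | 0.25 | 0.50 | 0.76 | 1.02 | 4.4 |
| 5% | 0.13 | 0.25 | 0.38 | 0.51 | 3.2 |

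Half-width = 1.96 × √(F(1−F)/175).

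**All three estimates on one horizon (day 395; F = 20%, D = 15%).**

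- Incidence to day 395: 0.5786 × (1 − 0.6588) = 19.7%.
- One minus Kaplan-Meier: 1 − exp(−0.2415) = 21.5%.
- Proportion: incidence to day 335 is 17.2% and 70.2% are alive and event-free then, so 19.7/(17.2 + 70.2) = 22.6%.

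The proportion is about 2.8 points too high and one minus Kaplan-Meier about 1.7.

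**ATK against BTK (all rates assumed).**

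- TLR 10% and 20% with mortality 3% and 15%: the gap is 10.0 points by Kaplan-Meier and 8.7 by incidence, a shift of 1.3 against a gap half-width of 7.4.
- TLR 15% in both with mortality 5% and 15%: 0 against −0.8 points.
- TLR 30% and 10% with mortality 5% and 15%: a shift of 0.05.
- TLR 10% and 20% with 15% mortality in both: incidence 9.24% and 18.52%. The relative overstatement is nearly the same (8.2% and 8.0%), so the relative comparison hardly moves, and the absolute gap goes from 10.0 to 9.3.

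**The case against.** The strongest reply is that nothing planned is invalid. Kaplan-Meier with deaths censored is a legitimate cause-specific summary, and two cohorts with the same TLR hazard should share that curve. The endpoints are secondary and descriptive, with no hypothesis. The numerical effect is small, and it understates freedom from TLR and amputation, so it cannot flatter the device. Eligibility also asks for a lifespan sufficient to complete the study and excludes acute limb ischemia and Rutherford category 6, which argues against the top of the assumed mortality range. Deaths are not hidden either: Protocol 8.5 requires every death to be reported, and SAP 9.7 counts discontinuations by reason.

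All of that stands, and it limits the point to a cheap improvement. It does not remove the gap. The SAP does not label the curves as cause-specific, the accompanying proportions are further from incidence than the curves are, and no output gives the incidence itself.

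A reader might infer three stronger things that the documents do not support.

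- **That censoring deaths distorts the ATK-BTK reading.** This needs mortality to differ between the cohorts, and no cohort mortality is given. The assumed scenarios move the gap by 0.05 to 1.3 points.
- **That the overstatement is always largest where mortality is highest.** That holds in relative terms. In points it also depends on event risk: 2% event risk with 20% mortality gives 0.2 points, while 20% with 5% mortality gives 0.5.
- **That a 14-point error is hidden in the amputation curve.** At 5% amputation and 15% mortality, freedom from amputation is 95.0%, and 0.95 × 0.85 = 80.8% are alive without amputation. These are two different estimands. The bias in amputation incidence in that case is about 0.4 points.

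**Conclusion.** The point holds as a gap in what is estimated, of modest numerical size. Event-free deaths are censored in both Kaplan-Meier analyses and, when they come before the lower window limit, removed from the proportions. Both estimates therefore exceed the actual incidence of TLR and of major amputation whenever subjects die, the proportions by more.

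For 12-month mortality of 5 to 20%, the excess of one minus Kaplan-Meier is 0.5 to 2.0 points at 20% TLR and about 0.1 to 0.5 at 5% amputation, in each case below the half-width for one cohort. These sizes rest on assumed rates and constant, independent hazards; the direction does not depend on the rates chosen. The primary endpoints are unaffected, and the relative ATK-BTK comparison would shift appreciably only if mortality differs between the cohorts.

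**What to change.** In SAP 6.2 and 6.3:

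1. State that event-free deaths are handled at the date of death from the Subject Disposition page, replacing the two clauses for these subjects.
2. Keep the Kaplan-Meier curves and label them as cause-specific with deaths censored.
3. Add the Aalen-Johansen cumulative incidence of TLR and of major amputation, with all-cause death as the competing event, at 30 days, 6 months and 12 months for ATK, BTK and All. Present it beside the evaluable-only proportions as the estimate of actual incidence.
4. As separate estimands, report amputation-free survival, and extend freedom from death from the DCB subgroup (SAP 7.3.3) to all ITT subjects by cohort.

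No new data are needed: every death must be reported under Protocol 8.5, and SAP 7.3.3 already computes time to death. The cost is SAP wording, one more table per endpoint, and a sentence explaining why the estimates differ.
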